**c. Measurements/End points:**

Primary efficacy end point is the proportion of patients with undetectable HCV PCR at 12 weeks after completion of HCV treatment with Sofosbuvir/Velpatasvir

Primary safety end point: The incidence of adverse events related to DAA treatment

Secondary end points:

eGFR and serum creatinine at 6 and 12 months post-transplant

Patient's survival at 6 and 12 months

Graft's survival at 12 months

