# **Study Protocol, Statistical Analysis Plan, and Informed Consent for**

## **Utilization of Hepatitis C Positive Kidneys in Negative Recipients**

### **(USE-Hep C)**

#### **I. Objectives**

To evaluate the safety and feasibility of transplanting kidneys from Hepatitis C virus (HCV) infected donors into recipients without HCV infection

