#### **II. Background and Rationale**

##### **a. Background**

Patients with end stage renal disease (ESRD) have increased mortality compared to their healthy peers with a five years survival chance of 42-52% in hemodialysis and peritoneal dialysis patients respectively. Over the last decade, the number of ESRD patients has risen significantly. In 2015, there was over 124,000 new cases and 703,243 prevalent cases of ESRD in the United States (1a). Kidney transplantation remains the preferred treatment modality. Successful kidney transplantation is associated with improved survival, improved quality of life and health care cost savings when compared to dialysis. However, the gap between patients in needs and available organs remains large. In 2017, there were over 94,000 patients waiting on the deceased donor kidney transplant waiting list with only 28,588 deceased donor transplantation performed(1). This organ shortage along with the advances in the available treatments of transmittable diseases such as human immunodeficiency virus (HIV) and hepatitis C virus (HCV) has prompted the transplant society to explore donors previously believed to be an acceptable candidate for donation.

Traditionally, HCV donor positive (HCV D+) kidneys were offered only to HCV positive recipients due to a 100% HCV transmission risk. Due to the low numbers of kidney transplant candidates who are also HCV positive, many of these kidneys are discarded. The development of direct acting anti-viral drugs (DAAs) have transformed the realm of HCV therapy. DAAs has turned HCV hepatitis into a highly curable condition with cure rates exceeding 95% for all different HCV genotypes 1 through 6(2-6).

DAAs can be safely used in all solid organ transplantation. Sofosbuvir/velpastasvir (Epclusa) combination was used for treatment of recurrent HCV infection (genotype 1 through 6) after liver transplantation (3, 5, 7). A 12 weeks treatment resulted in overall 96% cure rate in patients with and without cirrhosis. The drug combination was very well tolerated and had minimal interaction with immunosuppressants. Once daily Glecaprevir/pibrentasvir (Mavyret) combination was used to treat HCV infection (genotype 1 through 6) in 80 liver transplant and 20 kidney transplant recipients in the MAGELLAN-2 study(8). The overall cure rate was 98% at 12 weeks post-treatment. The drug combination was again very well tolerated.

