**b. Rationale:**

DAs are highly tolerated by patients and carry a cure rate of >95%. This favorable side effect profile and high efficacy can help expand the pool of available organs by increasing the utilization of organs from HCV infected donors. Over the past decade, the opioid crisis have increased the number of HCV infected deceased donors. These donors are usually young with fewer comorbid conditions such as diabetes and hypertension. Organ procured from such donors are usually of good quality. The transmission rate of HCV when using infected organ is guaranteed but the availability of DAs make this less of a concern. This scenario has been tested and proven safe by other groups. The EXPANDER (Exploring Renal Transplant Using Hepatitis C Infected Donors for HCV- Negative Recipients) group at Johns Hopkins University performed transplantation of kidneys from HCV+ into 10 HCV- recipients(9). The group used **elbasvir-grzoprevir** (supplemented with sofosbuvir for genotype 2, 3) started before transplant and continued for 12 weeks post-transplant. There were no treatment related adverse effects. HCV virus was undetectable with stable liver function in all recipients 12 weeks after completion of treatment.

Another group, the THINKER (Transplanting Hepatitis C kidneys Into Negative Kidney Recipient), from the University of Pennsylvania also used similar drug combination elbasvir-grazoprevir (Zepatier) in 20 HCV negative recipients who received kidneys from donor infected with HCV genotype -1(10). The group reported a 100% transmission rate of HCV with 100% cure rate as evident by undetectable HCV pcr in the blood 12 weeks post treatment. There were again no treatment related adverse events. Kidney allograft function was excellent at 6 and 12 months.

The use of HCV + donors into negative recipients has also been investigated in thoracic organ transplantation including heart (11) and lung (12, 13). Patients in these reports were treated by either Sofosbuvir/Ledipasvir (Harvoni) if they contacted HCV genotype 1 or Sofosbuvir/Velpatasvir if they contracted other genotypes. All of the reported cases had complete cure of HCV transmitted after transplant and no treatment associated adverse effects.

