**c. Significance:**

DAAs has the potential to turn HCV infection into a condition similar to cytomegalovirus (CMV) infection. Currently, it's a routine and completely acceptable practice to transplant organs from CMV+ donors to CMV- recipients. These recipients are at very high risk for CMV infection. In the absence of preventive measures, 40 to 100% off all kidney transplant patients will develop CMV infection and up to 67% will develop CMV disease that could be life threatening(14, 15). Such risk is greatly ameliorated by the presence of active treatment for CMV infection in the form of ganciclovir, cidofovir and foscarnet. Similarly, DAAs are effective and very well tolerated treatment that should make transplanting HCV positive organs into negative donors possible.

It is hard to accurately estimate the number of additional donors that could be available if HCV+ organs are being used routinely. It's estimated that between 2005 and 2014 about 4,144 kidneys from HCV+ donors were discarded(16). Many more kidneys from HCV infected donors were probably never procured because of fear of lack of appropriate recipients. Over 8000 lives could have been saved have these kidneys been utilized. Additionally, accepting kidneys from HCV+ donors can shorten patients waiting time on the deceased waiting list(17). This in turn results in improved survival and overall quality of life and decreased health care costs. A cost effectiveness analysis compared the cost associated with accepting HCV+ donor kidney followed by DAAs vs remaining on dialysis while awaiting for HCV- kidney found a total cost saving of about \$138,000 per patient(18).

We believe HCV positive donor organs are being underutilized in the current era of DAAs. We hope to provide further proof to the safety and utility of the strategy of transplanting HCV positive donor into negative recipient. We hope such proof will encourage transplant leaders, organ procurement organizations, and payers to invest into building an infrastructure that can turn such strategy into standard of care and ensure access and coverage for a variable selection of HCV therapies.

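### The only cure endpoint is tied to completed sofosbuvir/velpatasvir, although other DAAs are planned, so it does not give the cure rate among all recipients infected by the transplant

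*Combined protocol and SAP*

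**What the plan says.** Section III.c states: "Primary efficacy end point is the proportion of patients with undetectable HCV PCR at 12 weeks after completion of HCV treatment with Sofosbuvir/Velpatasvir". It names no denominator beyond patients. The secondary endpoints are kidney function, patient survival and graft survival, so nothing else in the list is virological. The other primary endpoint is not tied to one drug: "Primary safety end point: The incidence of adverse events related to DAA treatment".

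Section III.d.2.III makes sofosbuvir/velpatasvir first line. Glecaprevir/pibrentasvir is second line where the graft is slow to function or eGFR is below 30 at two weeks. Other approved DAAs are third line after insurance refusal or where an interaction is possible. The same section schedules a PCR 12 weeks after DAA therapy ends, whichever drug was given.

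The aim is put more widely than one drug. Section I reads: "To evaluate the safety and feasibility of transplanting kidneys from Hepatitis C virus (HCV) infected donors into recipients without HCV infection". Section II.c adds: "We hope to provide further proof to the safety and utility of the strategy of transplanting HCV positive donor into negative recipient". Section III.a calls sofosbuvir/velpatasvir the preferred treatment, not the only one.

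**The concern.** Taken literally, the single cure rate leaves out every recipient treated with another DAA. That group is not a random subset: second-line treatment is assigned by early graft function, which is known only after the transplant. If completion is read as a condition of entry, the rate also leaves out recipients who stop early, die or are never treated.

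The two primary endpoints then cover different people. A recipient on another DAA can add an adverse event to the safety result but cannot add a virological failure to the efficacy result.

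The kidney precedents in section II.b are described by cure in the whole group. For one, "HCV virus was undetectable with stable liver function in all recipients 12 weeks after completion of treatment", with a regimen that was "supplemented with sofosbuvir for genotype 2, 3". For the other, "The group reported a 100% transmission rate of HCV with 100% cure rate". A one-drug rate is not the same quantity, and it does not answer the strategy question in section II.c.

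**Working it through.** **Plan's own figure.** There is none to reproduce. Section III.b gives a target of 55 patients and says it does not come from a power analysis.

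**Inputs.** From the plan: N = 55 (III.b); transmission treated as certain (II.b); for sofosbuvir/velpatasvir, "A 12 weeks treatment resulted in overall 96% cure rate in patients with and without cirrhosis" (II.a); 98% for glecaprevir/pibrentasvir (II.a). Assumed, because the plan gives no values: the number on other DAAs, o (5 to 22 of 55); the number not completing; and any cure deficit on other DAAs.

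**Intervals.** Exact (Clopper-Pearson) 95%: lower limit is the 0.025 quantile of Beta(x, n−x+1), upper limit the 0.975 quantile of Beta(x+1, n−x). When x = n the lower limit is 0.025^(1/n), for example 0.025^(1/44) = 0.920.

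**Step 1. Can the endpoint register a failure on another DAA?** Assume 55 infected, 11 on other DAAs, and all 44 on sofosbuvir/velpatasvir cured.

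| Rate | All 11 others cured | 3 of the 11 fail |
|---|---|---|
| Sofosbuvir/velpatasvir recipients only | 44/44 = 100% (92.0 to 100) | 44/44 = 100% (92.0 to 100) |
| Sofosbuvir/velpatasvir cures over all 55 | 44/55 = 80% | 44/55 = 80% |
| Any DAA, all infected | 55/55 = 100% (93.5 to 100) | 52/55 = 94.5% (84.9 to 98.9) |

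Each such failure moves the any-DAA rate by 1/55 = 1.8 points and moves either reading of the stated endpoint by 0.

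**Step 2. Drug restriction alone, with stops and deaths counted alike.** Any-DAA rate = [0.96(55−o) + 0.98o]/55, against 0.96 for the one-drug rate. The gap is 0.02 × o/55.

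| o | Any-DAA rate | Gap (endpoint too low) | Gap if other DAAs cure 10 points worse (endpoint too high) |
|---|---|---|---|
| 5 | 96.2% | 0.2 points | 0.9 points |
| 11 | 96.4% | 0.4 points | 2.0 points |
| 17 | 96.6% | 0.6 points | 3.1 points |
| 22 | 96.8% | 0.8 points | 4.0 points |

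The last column is 10 × o/55. If 5% of each group stop or die uncured, both rates are multiplied by 0.95 and the first set of gaps is unchanged after rounding.

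**Step 3. Completer-only reading.** Of the 44, let 2 not complete and let everyone else, including the 11 on other DAAs, be cured. Completers give 42/42 = 100% (91.6 to 100).
- If both died or had no PCR, the any-DAA rate among all infected is 53/55 = 96.4% (87.5 to 99.6), and the rate among sofosbuvir/velpatasvir starters is 42/44 = 95.5% (84.5 to 99.4).
- If both stopped early but were undetectable 12 weeks after the last dose, the any-DAA rate is 55/55.

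The completer figure is therefore too high by 0 to 100 − 96.4 = 3.6 points.

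**Step 4. Can the wider endpoint be observed in time?** The latest case is a first positive PCR at 12 months, start within 8 weeks, 12 weeks of therapy (assumed for every DAA), then 12 weeks: 52 + 8 + 12 + 12 = 84 weeks, about 19 months. The clinic schedule in III.d.3 runs to 24 months.

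**The case against.** - **The denominator is undefined, so the direction of error is open.** This stands in part. If all 55 are the denominator, the endpoint is too low, not too high. But that reading gives 80% when every recipient is cured and still does not move when a recipient on another DAA fails, so it does not rescue the endpoint.
- **The completion wording may only fix the time of the PCR.** It may, and section II.b uses similar words for a whole-group result. Text may also be missing at the start of item III under Data and statistical analysis, where a rule for non-completers could have stood. The completer error is therefore conditional on that reading. The drug restriction does not depend on it.
- **On the plan's own cure rates the effect is trivial.** This stands: under 1 point, with the endpoint too low. Three failures among 11 is an unfavourable illustration; at 98% cure, three or more has a probability of about 0.1%. That 98%, however, comes from 80 liver and 20 kidney recipients in another study, not from a group selected here for poor early graft function or insurance refusal.
- **A drug-specific endpoint is a legitimate choice, and nothing is lost because the PCRs are collected anyway.** Legitimate as a secondary result. As the only cure endpoint it does not match the aim in sections I and II.c. In a mostly descriptive study the headline proportion is the main finding.
- **The precedents are not cleanly comparable anyway.** True: one began treatment before transplant and the other used genotype-1 donors only. The endpoint should not add a further, avoidable difference.

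**Conclusion.** The concern holds. No reading of the stated endpoint gives the cure rate among all infected recipients unless every one of them completes sofosbuvir/velpatasvir, and the plan itself expects that some will not receive it.

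The numerical effect cannot be fixed from the documents. With 5 to 22 of 55 on other DAAs, the drug restriction alone makes the rate 0.2 to 0.8 points too low at 96% and 98% cure, and 0.9 to 4.0 points too high if other DAAs cure 10 points worse. A completer-only reading with 2 of 44 not completing adds an error of 0 to 3.6 points. If the drugs cure about equally well, the main cost is precision. The firmer point is structural: a failure on another DAA cannot change the headline result. This should be corrected, but it is not fatal to the study.

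**What to change.** Redefine the primary efficacy endpoint as follows.

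- **Outcome:** undetectable HCV PCR 12 weeks after the end of the DAA course, whichever DAA is used.
- **Denominator:** all recipients of a PCR-positive kidney who have a positive post-transplant HCV PCR on the schedule in III.d.2.I. Report recipients who never turn positive separately.
- **Intercurrent events:** count death before that PCR, non-initiation and a missing PCR as not cured. For early stoppers, use a PCR timed 12 weeks from the last dose.
- **Reporting:** give the proportion with an exact 95% confidence interval. Keep the sofosbuvir/velpatasvir rate as a secondary result, with all who start that drug as its denominator.

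The cost is endpoint wording and a few PCRs timed from the last dose in early stoppers. The PCR 12 weeks after any DAA is already scheduled, and no treatment rule changes. The headline rate may come out slightly less favourable than a completer rate.

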### **III. Procedures**

**a. Research design:**

This will be an open label, prospective, interventional, proof of concept study to evaluate the feasibility and safety of kidney transplant from HCV positive donors into HCV negative donor using Sofosbuvir/Velpatasvir as the preferred treatment choice for post-transplant HCV transmission.

The Ohio (OSUMC) has performed HCV+ into HCV- recipient liver transplants as standard of care since February of 2019. OSUMC has also been performing transplant of liver and kidneys from donors who are HCV antibody positive but PCR negative (non-viremic donors) since 2016. In order to present an overall picture of the patient outcomes across multiple types of organ transplants using HCV+ organs, we would like to review data from these liver and kidney transplant patients. To do so, retrospective data from recipients of HCV positive into negative liver transplants, and HCV antibody positive but PCR negative liver and kidney transplant recipients will be analyzed. Patients who were treated between January 19th, 2016 and November 26th, 2019 will be included in our analysis.

In order to confirm the safety of transplants using HCV+ kidneys, we will compare the outcomes of transplant from HCV viremic donors (HCV PCR+) to those from HCV non viremic donors (donors with HCV antibody neg/PCR negative and HCV antibody positive/PCR negative). To do so, we will retrospectively review charts of patients who received a kidney transplant at OSU between 1/1/2018 and 8/1/2020. This review will include recipients of HCV antibody negative/PCR negative (antibody (ab)-/Nucleic Antigen Test (NAT)-), HCV antibody positive/PCR negative (ab+/Nat-), and HCV antibody positive/PCR positive (ab+/Nat+).

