**d. Detailed study procedures:**

After completion of post-transplant evaluation and signing informed consent, patient status at UNOS will be changed to "Willing to accept HCV+ organ". Once an organ become available, it will be offered to the patients on HCV+ list per UNOS points system. Care following receiving HCV+ donor kidney for study patients will be as follow

1. Induction/maintenance therapy:

- I. Patient will receive induction with Thymoglobulin (rabbit ATG) for a total dose of 4-6 mg/kg per routine center protocol. Thymoglobulin induction will be started on day 0 after transplant surgery.
- II. Maintenance immunosuppressive therapy: patient enrolled in the study will receive the same routine maintenance immunosuppressive therapy used for recipients of HCV negative kidneys in our center. Maintenance

therapy will be started on post-operative day 1 with Tacrolimus, Mycophenolic acid, and rapid prednisone taper. Tacrolimus will be started at a weight based total dose of 0.15 mg/kg divided into two daily doses 12 hours apart. Trough levels will be checked daily prior to morning dose while inpatient and dose will be adjusted to target trough level of 8-12 for the first three months. Trough levels target in enrolled patients will follow our center post-transplant Tacrolimus trough target. Mycophenolic acid will be started at dose of 720 mg twice daily on post-Operative day one and continued long term. Dose can be adjusted/reduced per patient's primary transplant physician as appropriate due to side effect or infectious complications. Prednisone therapy will be tapered off by day 4 per center protocol

2. Hepatitis C evaluation and treatment:

- I. Recipients will have HCV PCR checked on admission day 0 prior to kidney transplant, and on day 3 prior to discharge. Patient with negative HCV PCR prior to discharge will have PCR checked weekly for 8 weeks then monthly up to 12 months post-transplant until PCR is positive. Checks will be stopped once PCR is positive. Patients with positive HCV PCR at day 3 post-transplant will not have further weekly or monthly checks but will follow the during treatment/post-treatment HCV PCR schedule mentioned below in section 2.3.d.
- II. Hepatology consult will be placed automatically on day 0 of transplant index admission and again if the patient is symptomatic for HCV.
- III. Direct acting anti-viral drugs (DAAs) will be initiated within eight weeks of first positive HCV PCR.

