  - a. Sofosbuvir/Velpatasvir will be first line therapy. Treatment will be with one tablet a day for 12 weeks.
  - b. Glecacrevir/Pibrentasvir will be a second line therapy for patients with delayed graft function or poor graft function (eGFR <30) two weeks post-transplant. Glecacrevir/Pibrentasvir doesn't require renal dose adjustment. Treatment will be with 3 tablets daily for 12 weeks.
  - c. Other FDA approved DAAs could be utilized as potential third line therapies if the first and second line therapies are not approved by insurance or patient could have a potential drug to drug interactions
  - d. Patient will receive follow up HCV PCR on week 4 and week 12 of therapy. HCV PCR will be repeated on week 12 following completion of DAA therapy.

3. Clinic schedule follow up:

- I. Patient will be seen in the transplant clinic per routine post-transplant protocol; weekly x4, then on weeks 6, 9 and 12, then months 4,6,9 and 12, 18 and 24.

- II. Patient will be seen by Hepatology only if the patient is symptomatic for HCV.
- 4. Laboratory schedule:
  - I. Patient will have CBC, Chem-7, and Tacrolimus trough levels drawn twice weekly for the first 12 weeks, then once a week 3-6 months, then every two weeks 6-12 months, then once a month thereafter (standard of care)
  - II. Liver function test (LFTs), Prothrombin time (PT), and Partial Thromplastin Time (PTT) will be checked weekly for the first 12 weeks then quarterly per center protocol
  - III. HCV PCR will be checked on week 4 and week 12 of therapy. HCV PCR will be repeated on week 12 following completion of DAA therapy then quarterly for one year Lipid profile, HbA1c, iron studies and alloscreen will be checked per center protocol
- e. **Data and statistical analysis:**
  - I. Data presented will be mostly a descriptive data giving low number of enrolled patient and lack of adequate power analysis
  - II. We will collect the following data points for retrospective chart review:
    - a. **Recipient:** medical record number, transplant date, patient demographics, blood type, End-stage liver disease etiology, Model for end stage liver disease (MELD) score at transplant, end stage renal disease etiology, time of dialysis prior to transplant, CMV status for donor and recipient, Epstein-Barr virus (EBV) status, and post-transplant HCV activation, and post-transplant treatment information
    - b. **Donor:** demographics, cause of death, CMV status, EBV status, HCV genotype

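### The only adverse-event endpoint counts DAA-related events, so no listed endpoint captures non-fatal liver harm that is not attributed to the DAA

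*Combined protocol and SAP*

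**What the plan says.** The objective (section I) reads: "To evaluate the safety and feasibility of transplanting kidneys from Hepatitis C virus (HCV) infected donors into recipients without HCV infection". Section III.a repeats it as a study "to evaluate the feasibility and safety of kidney transplant from HCV positive donors into HCV negative donor".

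Section III.c then lists the endpoints. The only one about adverse events is "Primary safety end point: The incidence of adverse events related to DAA treatment". The primary efficacy endpoint is an undetectable PCR 12 weeks after Sofosbuvir/Velpatasvir. The secondary endpoints are eGFR and creatinine, "Patient's survival at 6 and 12 months", and graft survival at 12 months.

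Section III.d governs timing and monitoring:

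- Item 2.III: "Direct acting anti-viral drugs (DAAs) will be initiated within eight weeks of first positive HCV PCR".
- Item 2.I: a recipient who is PCR-negative at discharge "will have PCR checked weekly for 8 weeks then monthly up to 12 months post-transplant until PCR is positive".
- Item 2.II: "Hepatology consult will be placed automatically on day 0 of transplant index admission and again if the patient is symptomatic for HCV".
- Item 3.II: "Patient will be seen by Hepatology only if the patient is symptomatic for HCV".
- Item 4.II: liver function tests (LFT) and prothrombin time (PT) are drawn weekly for 12 weeks and quarterly after that.

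Section III.a also plans a chart-review comparison of viremic with non-viremic donors, offered as confirmation of safety.

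**The concern.** The question is about a transplant strategy. The safety endpoint is about a drug. An event before the first dose cannot be related to the drug, and an event put down to transmitted HCV is by that judgement not a drug event. Both fall outside the endpoint as worded.

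The plan itself foresees such events, since it provides for a further hepatology consult when HCV symptoms appear. Consider a recipient who develops symptomatic hepatitis or abnormal liver tests while waiting for the DAA, then clears the virus with kidney function and graft intact. Followed exactly, the plan counts that recipient as a success on every endpoint and as an event on none. The primary safety result would be a DAA tolerability rate, open to being read as the safety of using infected kidneys.

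**Working it through.** The plan gives no figure here to reproduce. The check is of endpoint coverage, then of dates.

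**Coverage.** Does each III.c endpoint capture a non-fatal liver event not attributed to the DAA?

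| Endpoint | Captures it? |
|---|---|
| PCR 12 weeks after Sofosbuvir/Velpatasvir | No: viral clearance |
| DAA-related adverse events | No: excluded by wording |
| eGFR and creatinine | No: kidney |
| Patient survival | No: fatal events only |
| Graft survival | No: kidney graft |

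None does.

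**Elsewhere in the plan.** The III.a comparison does not say which outcomes it compares. The chart-review data points in III.e include, after transplant, only HCV activation and treatment information. MELD is listed, but at transplant. No post-transplant liver test or liver event appears. The visible text of III.e names no analysis of the scheduled LFT/PT results.

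**Dates.** Inputs, all from III.d:

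- first post-transplant PCR on day 3;
- if negative, weekly PCR for 8 weeks, so the last weekly check is day 3 + 56 = 59;
- longest wait from first positive to first dose: 56 days;
- DAA course of 12 weeks = 84 days (first and second line);
- final PCR 84 days after completion;
- weekly LFT/PT on days 7, 14, ..., 84, reading the first 12 weeks as post-transplant.

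For a first positive on day d and a wait of w days, the time from transplant to 12 weeks after completion is d + w + 168, and the untreated share is w / (d + w + 168).

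- Treated on the day of the positive result: w = 0, share 0.
- d = 3, w = 56: first dose day 59; 56 / (3 + 56 + 168) = 56/227 = 24.7%. Weekly sets before the first dose: days 7 to 56, which is 8 of 12.
- d = 59, w = 56: first dose day 115; 56 / (59 + 56 + 168) = 56/283 = 19.8%. Weekly sets inside the interval: days 63, 70, 77 and 84, which is 4.

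The share rises with w and falls with d, so 24.7% is the largest value on this schedule. If the weekly checks are counted from transplant instead, the last is day 56 and the share is 56 / (56 + 56 + 168) = 56/280 = 20.0%, which changes little.

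**Weekly LFT cover of therapy.** Start on day 59: 84 − 59 = 25 of 84 days. Start on day 115: 0 of 84.

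**The case against.** **The plan has a strategy-level safety component.** The III.a comparison is meant for exactly this, and it has controls, which a single-arm endpoint lacks. That is a fair point about where the answer might come from. It does not close the gap while its outcomes are undefined and the data list holds no liver outcome. It does mean that the remedy should reach that comparison too.

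**Not being an endpoint is not the same as not being reported.** LFT and PT are scheduled, the analysis is descriptive, and part of III.e is blank in the text available. This stands as a limit on the claim: what can be said firmly is that III.c lists no such endpoint and the visible analysis text names none.

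**Eight weeks is a ceiling.** The background treats transmission as certain, so early detection is the expected course, and many recipients may start well before the limit. This stands, and the range accordingly starts at 0.

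**The window can be overstated.** A reader might count all time from transplant to first dose, giving 115/283 = 40.6% for a day-59 positive, with all 12 weekly LFT/PT sets before treatment. The documents do not support reading that as untreated infection: such a recipient was PCR-negative at the preceding weekly checks, and the wait after a first positive never exceeds 56 days.

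**It is a small proof-of-concept study.** True, and no power is claimed. Describing liver events needs none.

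**Conclusion.** The point holds. Section III.c contains no endpoint for non-fatal liver harm that is not attributed to the DAA, and the exclusion follows from the wording, not from missing detail. The interval in which an event is excluded purely because it precedes treatment runs from 0 to 56 days after a first positive PCR, at most 24.7% (day-3 positive) or 19.8% (day-59 positive) of the time to 12 weeks after therapy. This rests on a 12-week course, on treatment starting within the stated limit, and on weekly LFTs being counted from transplant. These are shares of time and scheduled data. The documents give neither a distribution of start dates nor a liver event rate, so no number of missed events can be stated.

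A reader might infer that liver harm would go unnoticed, or that the safety objective is not addressed at all. Neither follows. Liver tests are drawn and hepatology is consulted on day 0 and again on symptoms. Death, graft loss, kidney function, viral clearance and DAA-attributed liver events are all endpoints, and those results remain usable. The gap is in what must be counted, which leaves the safety question partly answered. It is a cheap improvement worth making.

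**What to change.** In III.c, keep the DAA-related endpoint but report it as DAA tolerability. Add a descriptive secondary safety endpoint in all recipients of a viremic kidney, counted from transplant to 12 months, or to 12 weeks after DAA completion if that is later:

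- (a) HCV-related or liver-related adverse events whatever their attribution, including any episode of HCV symptoms that triggers the repeat consult in III.d item 2.II. Show events before the first DAA dose separately, and record attribution with an uncertain category.
- (b) LFT/PT abnormalities from the tests already scheduled in III.d item 4.II, at a threshold the sponsor sets in advance.

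In III.a, use the same liver outcomes for the comparison of viremic with non-viremic donors where the charts hold them.

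For a start at the eight-week limit, the later end date applies only to first positives after day 365 − 168 − 56 = 141.

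The sample size, treatment timing, visits and blood draws stay as they are. The costs are some extra event recording, uncertain attribution under concurrent immunosuppression, and a possibly less favourable safety picture. Weekly LFTs also cover only part of a late-starting course, which should be stated as a limitation. A general requirement to collect all serious adverse events would go beyond this point and is not needed to meet it.
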